5.4.4 Research Blood Samples for all participants

The following research bloods samples, will be taken from all participants at study baseline, 12 and 24 weeks for mechanistic analysis and evaluation of immune response

- 1 x 6ml lithium heparin tube
- 2 x 4ml serum tubes
- 1 x 3ml RNA tube

Processing of blood samples at site

- 1 x 6ml lithium heparin tube
 - This sample will be used for immunophenotyping. Immediately after collection the blood tube should be mixed well by inverting 8-10 times.
 - Sample can be kept at room temperature prior to shipping
 - Sample should be shipped on the day of collection (see E-CLAD UK laboratory manual for details)
- 2 x 4ml serum tubes
 - These samples will be used for immune marker analysis
 - Samples should be left at room temperature for 30-60 mins before processing

- Processed samples should be stored in -80°C freezer then batch shipped (see E-CLAD UK laboratory manual for details)
- Any sample remaining after the separation of serum should be disposed of in accordance with local policy.
- 1 x 3ml RNA tube
 - This sample will be used for transcriptomics
 - After collection, the blood tube should be mixed well by shaking or briefly vortexing contents
 - Samples should be stored in -80°C freezer then batch shipped (see E-CLAD UK laboratory manual for details)

The research blood samples will be analysed by a central laboratory at either Newcastle University or a commercial laboratory called Melio Health.

The samples going to Melio Health (those in the lithium heparin tubes) must be received by them the day following collection (ideally within 24 hours of collection). As Melio Health is only able to accept samples Monday-Friday, this means that these samples will need to be collected Monday to Thursday. Royal Mail safe boxes will be used to send these samples using overnight next day delivery. Sites must ensure that they know what time the last post collection is from their hospital post room and ensure samples are at the post room in time for the last post. This may mean that a morning appointment for the baseline, 12 week and 24 week visit will be necessary.

For participants receiving ECP, these bloods should be taken prior to commencing the treatment cycle that coincides with the visit where research bloods are due. There should be a minimum of 10 days between the previous cycle of ECP finishing and the 12 week research bloods being collected.

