5.12 Withdrawal from Trial

Either the participant or the treating clinician may make the decision to withdraw the patient from the trial. Discontinuation of allocated trial ECP treatment or SOC treatment is not necessarily a withdrawal from the trial if the participant is willing to continue with trial visits where this is an option (see section 5.11). **Please note:** where trial treatment is being stopped due to non-response and need for rescue treatment, the participant must be fully withdrawn from the trial. Please see appendix 5 for non-responder decision tree.

If the participant is withdrawn from the trial, they cannot continue with ECP treatment and will be followed up for adverse event reporting purposes only for an additional 4 weeks from the point of stopping ECP. With participant consent, the week 24 research activities (see section 5.6) should be undertaken at the last study visit before withdrawal. If the participant is withdrawn after the baseline visit and before the week 12 visit then, with consent, the week 12 research blood samples should be collected at the last study visit before withdrawal. If the participant is withdrawn after the week 12 visit, then no further research blood samples are required.

All withdrawals from the trial should be asked if they allow the use of routinely collected data for the remainder of the trial follow up period

If the patient requests to withdraw from the mechanistic sub-study or qualitative sub-study, they can still remain in the main trial.

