8. TRIAL INTERVENTION

8.1 Description of Standard of Care

The management of lung transplant recipients both before and after the development of CLAD may vary subtly between the UK centres. However, the underlying principles are well aligned in terms of a standardised maintenance immunosuppression regime (cell cycle inhibitor, calcineurin inhibitor and corticosteroids) and prophylaxis against common viral, bacterial, and fungal infections with attention to blood pressure control, lipid profiles, preservation of renal function and bone protection. Acute cellular rejection of ISHLT grade A2 or higher is treated with short term augmentation of corticosteroids in all centres.

The diagnostic approach to new onset CLAD is also well aligned with the 2019 ISHLT criteria (3) with a diagnosis made only after a failed response to a trial of azithromycin therapy and exclusion of reversible causes such as cellular or humeral rejection, large airway anastomotic obstruction and infection. After a diagnosis of probable CLAD, patients are observed and those with progressive loss of lung function have traditionally been offered potential immunomodulatory therapy with either TLI or ECP depending on availability and funding. Other therapeutic approaches with little to no evidence to support them have generally been avoided. Retransplantation provides the only realistic therapeutic option in those who progress to very severe CLAD without significant other comorbidities.

All five centres participating in this trial have agreed clear principles for the SOC for CLAD treatment. The basis remains supportive with supplementary oxygen for hypoxia, prevention and treatment of infective exacerbations, physical rehabilitation, and psychosocial support. This will be the approach in both arms of the study with use of ECP in the treatment arm the only difference.

Participants will not be treated with any immunomodulatory interventions such as TLI or ECP as part of SOC in the trial. Only if there is rapidly progressive CLAD disease by 12 weeks as defined in the

protocol (>20% decline in FEV1 or FVC) will the patient leave the study and be eligible to access immunomodulatory interventions outside the study at the discretion of the clinical team. If at any point after 12 weeks, but before 24 weeks, they reach >20% decline in FEV1 then they will also have the option to leave the study and access immunomodulatory treatments at the discretion of the clinical team.

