10.3.3 Mechanistic analysis

We will conduct a range of analyses that will explore the mechanism of ECP.

1. To investigate which cell and molecular variables in blood (at baseline) are associated with response, we will fit regression models with responder/non-responder as an outcome and each potential biomarker included (in a separate model) as a baseline covariate.
2. To investigate the trajectories of the cell and molecular variables and how they differ in responders and non-responders, we will fit a longitudinal model for each variable with responder/non-responder as a covariate. This will be done in all patients and then separately in SOC and SOC+ECP patients.
3. To investigate the differential composition of circulating leukocytes, we will model the percentage of blood made up of each cell type and how these change from baseline over time in responders and non-responders using a longitudinal model as described above.
4. To investigate if differences in the transcriptional signature of leukocytes at baseline or changes over time are predictive of response, we will perform both single gene and effector pathway analysis in responders and non-responders across both study arms.
5. To investigate if there is a predictive signature associated with the treatment effect of ECP+SOC vs SOC, we will apply a method developed in Newcastle that extends the adaptive signature design (323). This may detect a 'sensitive' subgroup of patients who strongly benefit from ECP.

These analyses will be exploratory and will help inform a subsequent effectiveness study. The power of the mediation analyses depends on the proportion of responders and non-responders. Assuming

50% of patients are responders, we will have 90% power to detect standardised effect sizes of 0.7. For the Newcastle site, we anticipate a sample size of around 16, which would provide 90% power to detect standardised differences of 1.6. A multiple testing correction will be applied to ensure that the false discovery rate is controlled at 5%.

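### Participants who progress and leave between weeks 12 and 24 give no exit research blood, so late biomarker data are informatively missing among non-responders

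*Protocol*

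**What the plan says.** Protocol section 5.4.4 plans research blood at three times; the samples "will be taken from all participants at study baseline, 12 and 24 weeks for mechanistic analysis and evaluation of immune response". The schedule in section 5.4.1 agrees. Section 5.4.4 also asks for the week-12 sample from participants classed as non-responders at that visit.

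Section 5.12 sets three rules for participants who withdraw:
- For all leavers, "With participant consent, the week 24 research activities (see section 5.6) should be undertaken at the last study visit before withdrawal". The section 5.6 list contains full lung function, the walk test and the two questionnaires. It does not contain research bloods, although 5.4.1 and 5.4.4 schedule them at week 24.
- For those leaving between baseline and week 12, with consent, "the week 12 research blood samples should be collected at the last study visit before withdrawal".
- For later leavers, "If the participant is withdrawn after the week 12 visit, then no further research blood samples are required".

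Leaving is tied to progression. Sections 5.5.3 and 5.12 require full withdrawal when a non-responder is to receive rescue treatment, and section 5.11 ends trial visits once it has started. Section 8.1 adds that participants whose FEV1 falls by more than 20% between weeks 12 and 24 "they will also have the option to leave the study and access immunomodulatory treatments at the discretion of the clinical team".

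Among the mechanistic analyses in section 10.3.3 is a longitudinal model for each biomarker, with responder status as a covariate, fitted in all patients and then by arm. Its stated aim is: "To investigate the trajectories of the cell and molecular variables and how they differ in responders and non-responders".

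**The concern.** The protocol sees the value of sampling at failure. It does so at week 12, and it does so for early leavers. Only for failures after week 12 does it ask for nothing, at a visit where the other week-24 research assessments are to be done anyway.

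Take a participant who is stable at week 12, progresses by about week 18 and leaves for rescue treatment. The trial holds two samples from this person, at baseline and week 12, both taken before the failure. The late samples from non-responders then come only from those who did not leave. If leavers had a different immune course from those who stayed, the late non-responder trajectory describes the stayers.

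At stake is the first mechanistic objective in section 2.3.1, which compares immune responses in ECP responders, ECP non-responders and SOC participants. An analysis plan can model the gap but cannot recover a sample that was never drawn.

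**Working it through.** **1. Who has which samples under the current rules.**

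| Participant | Baseline | At or by week 12 | After week 12 |
|---|---|---|---|
| Leaves before week 12 | yes | yes, at last visit (5.12) | none due |
| Fails at week 12 and leaves then | yes | yes; this is the exit sample (5.4.4) | none |
| Fails after week 12 and leaves | yes | yes, before failure | **none (5.12)** |
| Non-responder who stays | yes | yes | yes, week 24 (5.4.1, 5.4.4) |
| Responder who stays | yes | yes | yes, week 24 |

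The third row is where no sample shows the immune state at failure.

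**2. The protocol's own power figure.** Section 10.3.3 assumes 50% responders and states 90% power for a standardised effect of 0.7. With 90 patients this is 45 v 45. It gives no significance level for this figure, so I assume two-sided 5% and no multiplicity correction. The normal approximation is

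power = Φ( d / √(1/n₁ + 1/n₂) − 1.96 )

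with d = 0.7 and n₁ = n₂ = 45: √(1/45 + 1/45) = 0.211; 0.7/0.211 = 3.32; Φ(3.32 − 1.96) = 91.3%. The stated 90% is reproduced, and it counts every patient as sampled.

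**3. Loss of precision if late samples are missing.** Let w be the share of non-responders without late blood. The documents give no value, so w is an assumption. The contrast is a simple late comparison of 45 responders with 45(1 − w) non-responders, d = 0.7.

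| w | Non-responders with late blood | Standard error (SD units) | Power | Effect detectable with 90% power |
|---|---|---|---|---|
| 0 | 45 | 0.211 | 91.3% | 0.68 |
| 20% | 36 | 0.224 | 87.9% | 0.72 |
| 40% | 27 | 0.243 | 82.0% | 0.79 |
| 60% | 18 | 0.279 | 70.9% | 0.90 |

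The within-arm models start from lower power. At the planning rates in section 10.1 (55% and 30% responders, 45 per arm), the ECP arm has 24.75 v 20.25. Power at d = 0.7 is 64.7% with no loss and 51.5% at w = 40%. The SOC arm has 13.5 v 31.5, with power 57.6% and 50.2%.

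**4. Possible bias.** If leavers differ from remaining non-responders by g standard deviations at the late time, the mean of the observed late non-responder values is off by w × g. At w = 40% and g = 0.5 to 1.0 (both assumed), that is 0.4 × 0.5 = 0.2 to 0.4 × 1.0 = 0.4 SD, against a planned detectable effect of 0.7 SD. This is the error of a complete-case mean. A longitudinal model that uses the earlier samples would remove whatever part of it those samples predict.

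**The case against.** A reader might infer that the trajectory comparison loses its key group. The documents do not support that. Non-responders identified by week 12 are sampled then. Leaving after week 12 on a 20% FEV1 fall is optional (section 8.1), ECP may continue after non-response (sections 1.3 and 5.4.5), and section 7.3 also counts as a non-responder anyone with more than 10% loss due to progressive CLAD at week 24. Those who stay give week-24 blood. Late leavers keep two samples and still enter the model, and the analysis of baseline predictors is untouched.

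The bias argument also has limits. Responder status is a covariate in the model, and missingness that depends only on a modelled covariate does not by itself bias the contrast. Bias needs selection among non-responders beyond what their baseline and week-12 values show. That is plausible, since leaving follows worsening after week 12, but the documents cannot show it.

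The power figures describe a cross-sectional contrast; the plan is longitudinal and uses every visit, so the real loss should be smaller. They also do not separate participants who failed at week 12, already sampled at failure, from later failures.

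The remedy is partial. Week 24 falls four weeks after the last scheduled ECP cycle (section 3.1), whereas an exit sample may fall mid-course, and one taken soon after week 12 adds little. Some leavers will refuse consent or be too ill. The protocol calls these analyses exploratory, and the primary, secondary and safety analyses are unaffected.

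All of this stands, and it sets the scale of the point. It does not explain why blood is the one research item not asked for at a late withdrawal visit. That 5.12 does not forbid a sample is little help, because sites will not routinely draw one that they are told is not needed.

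**Conclusion.** The point holds in a limited form. Section 5.12 treats late leavers differently from early leavers, and blood differently from the other week-24 assessments. Because leaving after week 12 is tied to progression and rescue, late biomarker values will be informatively missing for participants who fail and leave between weeks 12 and 24. This weakens the late part of the responder versus non-responder trajectory comparison and may bias it; it does not remove the comparison.

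The size cannot be fixed from the protocol. The fall from about 91% power to between 88% and 71% rests on an assumed 20% to 60% of non-responders without late blood, and on a simple two-group contrast. The 0.2 to 0.4 SD shift rests on two further assumptions and applies to a complete-case mean. Both are illustrations, not predictions. The change is a cheap improvement to an exploratory analysis.

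**What to change.** Amend section 5.12 so that participants withdrawn after the week-12 visit and before week 24 have, with consent, the research blood set taken together with the section 5.6 assessments at the last visit before withdrawal and before any rescue treatment. Exempt those whose last visit is the week-12 visit already sampled. Record the actual sampling date and the days since the last ECP treatment. Add research bloods to the section 5.6 list so that it matches 5.4.1 and 5.4.4.

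In the longitudinal models, use actual sampling time, treat these as exit samples and not as week-24 values, and state how informative dropout is handled.

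The cost is one blood set of 17 ml (6 + 2 × 4 + 3 ml), already planned for week 24, at a visit already designated for research assessments. Timing relative to ECP will vary. Some heparin tubes will be missed because section 5.4.4 limits their collection to Monday to Thursday; the serum and RNA tubes are stored frozen and batch shipped, so they can still be taken.

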5.12.1. Participant Requested Withdrawal from the trial

Participants have the right to fully withdraw from the trial at any time without having to give a reason. When a participant states they want to withdraw from the trial, sites should try to ascertain the reason for withdrawal and document this reason within the withdrawal form eCRF and participant's medical records.

Where a participant withdraws consent, no further research assessments will take place and the participant should be asked if they will allow the use of routinely collected data until the end of the trial follow up period. Data collected up to the point of withdrawal will be retained and included in the analyses. The participant's decision to allow the use of routinely collected data or not should be clearly documented.

5.12.2. Investigator Led Withdrawal from the trial

The investigator/treating clinician may withdraw a participant from the trial at any time if they deem it necessary for the following reasons:

- Continuing to attend trial visits and undergoing trial assessments would place unreasonable demands on the physical or psychological health of the participant. If participant and investigator agree, any assessments occurring as part of routine care would also be recorded in the eCRF.

- The participant loses capacity for a prolonged period.
- An adverse event, which results in inability to continue to comply with trial procedures.
- Inability to secure appropriate vascular access for ECP treatment to be delivered to participant in the ECP+SOC arm.
- Pregnancy.
- Significant protocol deviation or non-compliance.
- Termination of the clinical trial by the Sponsor.

Where the decision is taken by the clinician to fully withdraw the participant from the trial, the following procedures will apply:

- If the participant has not yet received any ECP treatment, the participant should not participate in any further trial-related procedures.
- If the participant has received any ECP treatment including IMP administration as part of the process, the ECP treatment should be stopped, and followed up for adverse event reporting purposes only for an additional 4 weeks.

Information that a participant has received ECP treatment even if incorrectly enrolled/randomised must be documented in the eCRF.

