5.12.3 Replacement of withdrawn participants

Participants who withdraw from the trial will be replaced in certain circumstances, and each case will be assessed individually.

A participant who is withdrawn in any of the following situations may be replaced:

- The participant is withdrawn from the trial prior to attending the next visit following their baseline assessment.
- The participant is found to be pregnant during the baseline assessment.
- The safety bloods taken at baseline show that the participant is ineligible for the trial.

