13.5 Protocol Compliance

It is the responsibility of the CI to ensure that the trial is run in accordance with GCP and the protocol. Trial tasks may be delegated to a suitably qualified or experienced member of the trial team, but the CI and PI will retain overall responsibility for adherence to protocol and GCP. The trial will be monitored by NCTU staff, to measure protocol compliance and manage deviations.

Prospective, planned deviations or waivers to the protocol are not allowed under the UK regulations on Clinical Trials. The CI will not implement any deviation from the protocol without agreement from the Sponsor, except where necessary to eliminate an immediate hazard to trial participants.

In the event of a deviation from the protocol, the nature of and reasons for the deviation will be recorded on a deviation tracking log and signed off by the PI and NCTU will notify the Sponsor. If this necessitates a subsequent protocol amendment, this will be submitted to the Sponsor for approval and then to the appropriate REC, MHRA and local NHS R&D for review and approvals as appropriate. It is Sponsor policy that waivers to the protocol will not be approved.

For the purpose of avoiding uncertainty, the occurrence of a protocol deviation, violation or serious breach will not lead to withdrawal of the participant from the trial. Once randomised, participants will remain in the trial unless meeting the criteria for withdrawal given in section 5.8.

For sites where the ECP unit falls within a different trust to the research team, if any deviations should occur while the participant is with ECP team/during delivery of ECP treatment, the ECP team must ensure these details are emailed to the research team in a timely manner.

The research team will then include this deviation on the site deviation log and send the updated log to the central trial management team as per usual process.

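### Section 5.12.2 allows full withdrawal for protocol deviation, against 13.5, and for failed vascular access, which can cost the 24-week outcome in the ECP arm only

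*Protocol*

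**What the plan says.** **Withdrawal by the investigator (5.12.2).** Listed reasons for withdrawing a patient from the trial include "Inability to secure appropriate vascular access for ECP treatment to be delivered to participant in the ECP+SOC arm" and "Significant protocol deviation or non-compliance". The listing is permissive: the investigator may act on it if judged necessary. The consequences are stated as:

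- before any ECP: "If the participant has not yet received any ECP treatment, the participant should not participate in any further trial-related procedures";
- after some ECP: "the ECP treatment should be stopped, and followed up for adverse event reporting purposes only for an additional 4 weeks".

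**Protocol compliance (13.5).** Here "the occurrence of a protocol deviation, violation or serious breach will not lead to withdrawal of the participant from the trial". The next sentence reads "Once randomised, participants will remain in the trial unless meeting the criteria for withdrawal given in section 5.8". Section 5.8 deals with visits that a patient cannot attend and holds no withdrawal criteria; those are in 5.12.

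**Stopping treatment (5.11).** Patients who choose to stop allocated treatment for reasons other than disease progression are encouraged to keep their remaining visits and assessments.

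**Outcome and population.** Section 3.4.1 takes the baseline and 24-week FEV1 and FVC from full pulmonary function tests done as research assessments, and the 12-week values from routine clinical spirometry. Section 10.2 sets an intention-to-treat analysis of everyone recruited, protocol violators included.

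**Softening provisions.** Under 5.6 and 5.12 the week-24 assessments are brought forward to the last visit before withdrawal, with consent, and withdrawn patients are asked to allow use of routine data.

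**Replacement (5.12.3).** A patient may be replaced if "The participant is withdrawn from the trial prior to attending the next visit following their baseline assessment". Section 5.3.2 places randomisation at the baseline visit.

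**The concern.** There are two separate faults.

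First, a site faced with a serious deviation finds one section that permits withdrawal from the trial and another that rules it out, and the second refers it to a section with no criteria. Sites can then act differently on identical cases.

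Second, access failure is a treatment-delivery problem that only ECP-arm patients can have, yet it is listed as a reason to leave the trial and not merely to stop ECP. A control patient has no matching route out. Used as written, it removes the 24-week research measurement from one arm for a post-randomisation reason. An intention-to-treat comparison needs outcomes on patients who could not be treated as well as on those who could. Whether that outcome is measured should not depend on whether the patient or the investigator took the decision to stop.

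**Working it through.** **1. The texts side by side**

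| Event | 5.12.2 | Other section |
|---|---|---|
| Significant deviation or non-compliance | may be withdrawn from the trial | 13.5: does not lead to withdrawal |
| ECP cannot be delivered (access) | may be withdrawn from the trial | 5.11: patients who choose to stop treatment are encouraged to keep visits |
| Where the criteria are | 5.12.2 itself | 13.5 points to 5.8, which has none |

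The first row is a direct contradiction. The second is a poor fit: 13.5 concerns deviations, so the access reason does not breach its wording.

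**2. What is lost**

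- *12 weeks:* routine spirometry, recoverable if the patient allows use of routine data.
- *24 weeks:* the research test. A test brought forward to withdrawal is not a 24-week value. If access fails before cycle 1, the last study visit may be baseline itself, leaving nothing after randomisation. Routine week-24 spirometry may exist, but 3.4.1 does not name it as the source.

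**3. The plan's own figure**

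Inputs from 10.1: 90 patients 1:1 (45 per arm), response 30% and 55%, one-sided 5%, stated power 80%. By normal approximation with unpooled variance:

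0.25 / √[(0.30×0.70 + 0.55×0.45)/45] − 1.645 = 0.25/0.1008 − 1.645 = 0.834, so power is 79.8%.

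This reproduces the plan. Exact enumeration of Barnard's test (ordered by the z statistic, maximised over the common rate) gives 76.9%, the reference for step 5.

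**4. Type I error, illustrative**

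Assumption: *k* of 45 ECP patients are withdrawn for access failure. The documents give no rate. The true rate is 30% in both arms.

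- *Access failure unrelated to prognosis, patients left out:* the expected ECP rate stays at 30%. The test is level-controlled: exact type I error at a 30% rate is 4.2% for k = 2 and 4.8% for k = 5.
- *All k would have failed and are left out* (adverse end): apparent ECP rate q = 0.30×45/(45−k). Normal approximation: Φ[(q−0.30)/SE − 1.645], SE = √[0.21/45 + q(1−q)/(45−k)].
  - k = 2: q = 13.5/43 = 0.314, SE = 0.0984, result 6.6%; exact Barnard 5.6%.
  - k = 5: q = 13.5/40 = 0.3375, SE = 0.1013, result 10.1%; exact Barnard 9.9%.

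**5. Power if they are counted or followed instead**

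Exact Barnard, 55% in treated ECP patients, 76.9% when k = 0:

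| k | Counted as failures: ECP rate | Power | Followed, responding at 30%: ECP rate | Power |
|---|---|---|---|---|
| 2 | 0.55×43/45 = 52.6% | 69.7% | (0.55×43 + 0.30×2)/45 = 53.9% | 73.8% |
| 5 | 0.55×40/45 = 48.9% | 57.1% | (0.55×40 + 0.30×5)/45 = 52.2% | 68.6% |

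These use Barnard's test, on which 10.1 bases the sample size. The planned primary analysis is the augmented binary method, so they show order of magnitude only.

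**The case against.** The best defence is that the problem is small and partly handled. Inadequate access is an exclusion criterion (4.2), access is checked at baseline (5.2.4), and central catheters, ports and fistulae are allowed (8.2.3 and 8.2.4). Withdrawal is discretionary, and 5.12 says that stopping treatment is not necessarily withdrawal, so a patient with failed access can already stay in follow-up. All of this stands. It limits the number affected but does not reconcile the sections.

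Several stronger readings are tempting and are not supported:

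- *The rule biases the result towards ECP.* The protocol does not say how the model treats these patients. Section 10.3.5 foresees checking whether missingness is informative. If they are counted as failures, the effect runs against ECP. Nothing in the document links access failure to prognosis.
- *The 12-week outcome is lost too.* It comes from routine spirometry and can be kept with the patient's agreement.
- *Several reasons are specific to ECP.* Only vascular access is. The adverse-event criterion concerns inability to comply with trial procedures, and continued visits cannot sensibly be required there.
- *Replacement takes patients out of the intention-to-treat set.* Section 10.2 keeps everyone recruited, so replacement only adds patients. The remaining weakness is that 5.12.3 does not say so.

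**Conclusion.** The point holds as a conflict between sections and an avoidable, arm-specific loss of primary-outcome data. The contradiction between 5.12.2 and 13.5 on deviations, and the wrong reference to 5.8, are plain on the text and rest on no assumption. The access reason is a design weakness: it can remove the 24-week research test in the ECP arm only, and neither softening provision supplies that value.

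The size and direction of any bias are unknown. Numbers should be small. The range from about 5% to 9.9% for type I error rests on my assumption of up to 5 of 45 affected. Its upper end also requires that every one would have failed and is left out of the analysis. It is not a prediction. A reader might infer that the trial's false-positive rate is inflated; the documents do not support that. They do support correcting the wording, because the correction is cheap and removes the question.

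**What to change.** - **Reconcile 5.11, 5.12.2 and 13.5.** Handle vascular access failure and deviation or non-compliance as discontinuation of allocated treatment. Keep the scheduled week-12 and week-24 outcome assessments for every randomised patient who has not withdrawn consent and is able to attend.
- **Correct 13.5** so that it refers to the section that holds the withdrawal criteria (5.12), not 5.8.
- **Add to 5.12.3** that any randomised patient who is replaced stays in the full analysis population.
- **Leave the adverse-event criterion as it is.** The change concerns data collection only, and no treatment decision is altered.

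The cost is an amendment of wording and a few patients attending visits that are already scheduled. Where these patients respond at the control rate, the intention-to-treat difference will be diluted, as the last columns of the power table show. That dilution belongs to the comparison that 10.2 sets out.
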